1.3. Rationale for This Study

Andecaliximab was first evaluated in subjects with cancer in the Phase 1 Study GS-US-296-0101. That study was divided into 2 parts: a monotherapy dose finding stage enrolling subjects with advanced solid tumors who had failed or were intolerant to standard therapy or for whom no standard therapy was available and a combination stage evaluating the safety and efficacy of andecaliximab at the dose determined from the monotherapy stage with available chemotherapies in subjects with advanced pancreatic, non-small cell lung cancer (NSCLC), human epidermal growth factor 2 (HER2) negative gastric/GEJ adenocarcinoma, colorectal, and breast cancer.

Results from non-Japanese subjects with HER2 negative advanced gastric/GEJ adenocarcinoma treated with andecaliximab 800 mg IV Q2W and mFOLFOX6 in the Phase 1 Study GS-US-296-0101 demonstrated anti-tumor efficacy with an acceptable toxicity profile {[Shah 2017](#)}.

To enable clinical investigation of andecaliximab in Japan, Gilead is evaluating the safety and PK profile of andecaliximab as monotherapy and in combination with anti-cancer agents in Japanese subjects with advanced gastric/GEJ adenocarcinoma.

Rationale for Andecaliximab Dose Levels in Japanese Subjects

The first dose level of andecaliximab monotherapy in this study will be 800 mg IV Q2W. This dose was selected based on data from the dose-finding phase of the GS-US-296-0101 study. No DLTs were observed at andecaliximab doses up to 1800 mg IV Q2W. Based on safety and PK data from the dose finding phase of Study GS-US-296-0101, andecaliximab 800 mg IV Q2W was selected for the combination phase of the study for subjects with advanced gastric/GEJ

adenocarcinoma, pancreatic adenocarcinoma, colorectal adenocarcinoma and breast cancer. Data from these cohorts suggested andecaliximab 800 mg IV Q2W in combination with other anti-cancer agents was well tolerated and no new safety signal was identified compared to historic data from similar populations. Clinically relevant differences in andecaliximab PK between Japanese and Western subjects are not expected and it is anticipated that andecaliximab 800 mg IV Q2W monotherapy will be well tolerated in Japanese subjects.

Subjects enrolled in the monotherapy cohort(s) of this study will be evaluated in a 28-day DLT window. Safety and tolerability will be assessed after all subjects have been followed for at least 28 days after the first infusion of andecaliximab. If 2 or more subjects within the cohort of 6 subjects experience DLTs during the first 28 days of andecaliximab dosing, 6 additional subjects will be enrolled at a reduced dose of 600 mg Q2W. If 2 additional DLTs are reported at the 600 mg Q2W dose level, andecaliximab will be considered unsafe and will be discontinued.

Once all subjects in Cohort 1 have completed the 28-day DLT assessment period, an internal safety review team (SRT) will conduct a review of the safety and PK data from all subjects prior to opening the combination therapy cohorts.

In Study GS-US-296-0101, andecaliximab was administered at 1200 mg IV Q3W in combination with chemotherapy for subjects with advanced NSCLC (carboplatin plus pemetrexed for adenocarcinoma (n = 10) and carboplatin plus paclitaxel for squamous histology (n = 10)). Data from these cohorts suggested Q3W dosing of andecaliximab was well tolerated and no new safety signal was identified compared to historic data of carboplatin, paclitaxel, and pemetrexed in a similar population.

Finally, PK data from Study GS-US-296-0101 demonstrated similar trough plasma concentrations of andecaliximab in subjects with advanced pancreatic, gastric/GEJ adenocarcinoma and NSCLC following 800 mg IV Q2W or 1200 mg IV Q3W dosing irrespective of tumor histology or chemotherapy combination. These data support the use of these two alternate doses and schedules to facilitate co-administration with chemotherapies using either Q2W or Q3W dosing.

The SRT completed their review of all available clinical safety and PK data for 6 DLT-evaluable subjects in Cohort 1 on 11 May 2017 and determined the dose for the combination therapy cohorts (Cohorts 2 and 4) to be 800 mg andecaliximab Q2W, and Cohort 3 to be 1200 mg Q3W.

Rationale for Combination Therapy Cohorts in Japanese Subjects:

The combination therapy cohorts (Cohorts 2-4) will evaluate the safety and tolerability of andecaliximab in combination with the following anti-cancer regimens:

[figure not shown]
- Andecaliximab and SP in subjects with treatment-naïve advanced gastric/GEJ adenocarcinoma (Cohort 2)
- Andecaliximab and SOX in subjects with treatment-naïve advanced gastric/GEJ adenocarcinoma (Cohort 3)

- Andecaliximab and nivolumab in subjects with advanced gastric/GEJ adenocarcinoma who have progressed on an least 1 prior systemic therapy or line of treatment for unresectable/metastatic disease (Cohort 4)

The SP and SOX regimen were selected for evaluation based on Phase 3 studies of Japanese patients with advanced gastric/GEJ adenocarcinoma and national guidelines {[Koizumi 2008](#)}. The safety profile of andecaliximab and a fluoropyrimidine and platinum based regimen has previously been characterized {[Shah 2017](#)}.

Nivolumab is a human monoclonal antibody directed against PD-1 that blocks the interaction of PD-1 with PD-L1 and PD-L2 which has demonstrated activity in previously treated advanced gastric cancer {[Kang 2017](#), [Le 2015](#)}. Preclinical data suggesting that inhibition of MMP9 activity within tumors may re-balance a myeloid-rich tumor-associated cellular milieu to one that is less repressive to cytotoxic T-cell entry and activity. Additionally, the presence of myeloid suppressor cells may confer resistance to immune checkpoint directed therapy. An anti-MMP9 directed murine surrogate of andecaliximab has shown significant anti-tumor activity in models in which MMP9 is produced by infiltrating myeloid cells. Its anti-tumor activity is associated with reduction of tumor-associated fibrillar collagen and alterations in the immune cell transcript profile in the treated tumors. Inhibition of PD-1 on T cells in the presence of andecaliximab may allow for greater infiltration of activated lymphocytes into the tumor and augment the anti-tumor effect offered by a PD-1 inhibitor alone. This potential synergy provides rationale for combining andecaliximab and nivolumab in subjects with advanced gastric/GEJ adenocarcinoma (see [Figure 1-3](#)).

Figure 1-3. Hypothesis for synergy between andecaliximab and nivolumab

Hypothesis for the combination of andecaliximab with nivolumab (figure adapted from Gajewski et al Nature Immunology, {[Gajewski 2013](#)}). Treatment with andecaliximab could convert “type b” tumors with dense fibrotic stroma, high myeloid suppressor cell contact, and deficiency of T-cell infiltration into “type a” tumors in which T-cell entry is enabled via remodeling of the microenvironment and re-balancing of suppressive myeloid-derived cytokines and chemokines. T cells in “type a” tumors are susceptible to checkpoint inhibition, which is overcome by treatment with nivolumab.

1.4. Risk/Benefit Assessment for the Study

In Western subjects with advanced solid tumors, there were no DLTs observed with andecaliximab monotherapy doses of up to 1800 mg Q2W. Additionally, combining andecaliximab 800 mg IV Q2W or 1200 mg Q3W with available chemotherapy regimens in non-Japanese subjects with advanced solid tumors enrolled in Study GS-US-296-0101 appeared safe and well-tolerated.

The safety and efficacy profile of SP and SOX in Japanese subjects with advanced gastric/GEJ adenocarcinoma has been established {[Koizumi 2008](#), [Yamada 2015](#)}. Phase 1 data combining andecaliximab and mFOLFOX6 in advanced gastric/GEJ adenocarcinoma suggests clinical activity with an acceptable safety profile {[Shah 2017](#)}. These data support combining andecaliximab with fluoropyrimidine and platinum doublets commonly used in Japanese subjects with gastric/GEJ adenocarcinoma.

Phase 3 data demonstrating activity and safety of nivolumab monotherapy in Asian subjects with previously treated advanced gastric/GEJ adenocarcinoma {[Kang 2017](#)}, preclinical data suggesting potential synergy between andecaliximab and nivolumab, and safety data from the ongoing Phase 2 Study GS-US-296-2013 combining nivolumab and andecaliximab in a similar non-Japanese population (subjects with inoperable locally advanced or metastatic gastric/GEJ adenocarcinoma who have progressed on at least 1 prior systemic therapy or line of treatment for unresectable/metastatic disease) support evaluating the combination in a Japanese population.

Thus, the favorable nonclinical and clinical data outweigh the risks associated with administration of andecaliximab and hence support the evaluation of andecaliximab as monotherapy or in combination with anti-cancer agents in Japanese subjects with advanced gastric/GEJ adenocarcinoma.

1.5. Compliance

This study will be conducted in compliance with this protocol, Good Clinical Practice (GCP), and all applicable regulatory requirements.

2. OBJECTIVES

The primary objective of this study is:

- To characterize the safety and tolerability of andecaliximab as monotherapy and in combination with anti-cancer agents in Japanese subjects with inoperable advanced or recurrent gastric or GEJ adenocarcinoma

The secondary objectives of this study are:

- To characterize the PK of andecaliximab
- To evaluate the formation of anti-andecaliximab antibodies

The exploratory objectives of this study are:

- [REDACTED]
- [REDACTED]
- [REDACTED]

3. STUDY DESIGN

3.1. Endpoints

The endpoints for this study are described in Sections 8.1.2, 8.1.3, and 8.1.4.

3.2. Study Design

This is a Phase 1b, open-label, multicenter study to evaluate the safety and tolerability of andecaliximab as monotherapy and in combination with anti-cancer agents in Japanese subjects with inoperable advanced or recurrent gastric or GEJ adenocarcinoma. The study will comprise 4 cohorts, 1 monotherapy cohort, and 3 combination therapy cohorts.

Cohort 1 is andecaliximab monotherapy. Cohort 2 is combination therapy of andecaliximab with SP. Cohort 3 is combination therapy of andecaliximab with SOX. Cohort 4 is combination therapy of andecaliximab and nivolumab. Up to 38 subjects are expected to be enrolled in the study.

For Cohorts 1, 2, and 4, computed tomography (CT) or magnetic resonance imaging (MRI) scans will be performed every 8 weeks to evaluate response to treatment by RECIST v1.1. For Cohort 4, response to treatment will also be evaluated using immune-related response criteria recommendations {[Wolchok 2009](#)}.

For Cohort 3, CT or MRI scans will be performed every 9 weeks to evaluate response to treatment by RECIST v1.1.

Cohort 1: Andecaliximab Monotherapy

Up to 6 Japanese subjects with inoperable advanced or recurrent gastric or GEJ tumors will be enrolled to receive andecaliximab 800 mg via IV infusion over approximately 30 (\pm 5) minutes Q2W until disease progression.

The DLT assessment window is 28 days. The safety and tolerability of the 800 mg dose will be assessed after all 6 subjects have been followed for at least 28 days after the first infusion of andecaliximab. If 2 or more subjects within the cohort of 6 subjects experience DLTs during the first 28 days of andecaliximab dosing, up to 6 additional subjects will be enrolled at a reduced dose of 600 mg Q2W. If 2 additional DLTs occur at 600 mg, andecaliximab will be considered unsafe and will be discontinued. Therefore, a total of up to 12 subjects may be enrolled in Cohort 1.

A DLT is a toxicity defined below, considered possibly related to andecaliximab occurring during the DLT assessment window (Day 1 through Day 28).

- Grade 4 neutropenia (absolute neutrophil count [ANC] $<$ 500/ μ L) for $>$ 7 days, or febrile neutropenia (per the National Cancer Institute (NCI) Common Terminology Criteria for Adverse Events (CTCAE) Version 4.03 definition) regardless of duration

- Primary prophylaxis with granulocyte-colony stimulating factor (G-CSF) is not permitted during the first cycle of study treatment. G-CSF may be used at any time at the discretion of the investigator in response to treatment emergent neutropenia. Subjects who develop Grade 4 neutropenia related to andecaliximab will be considered a DLT (subjects may receive G-CSF at the discretion of the investigator in response to treatment emergent neutropenia).
- Grade 4 thrombocytopenia, Grade 3 thrombocytopenia associated with bleeding, or Grade 3 or 4 thrombocytopenia requiring platelet transfusion
- Grade 3 or 4 non-hematologic toxicity (excluding rash, nausea, diarrhea, and vomiting if controlled with standard supportive care)
- Non-hematologic toxicity of \geq Grade 2 (at any time during treatment) that, in the judgment of the investigator and the medical monitor, is dose-limiting
- Treatment delay of $>$ 14 days due to unresolved toxicity
- For certain toxicities such as laboratory assessments without a clear clinical correlate, a discussion between the investigator, medical monitor, and the sponsor may take place to determine if this adverse event (AE) should be assessed as a DLT necessitating dose reduction

After all 6 subjects in Cohort 1 have completed the 28-day DLT assessment window and 1 or 0 out of 6 subjects experienced DLTs, an internal SRT will conduct a review of the safety and PK data from all subjects prior to proceeding with the combination therapy cohorts to evaluate andecaliximab with other anti-cancer agents.

The SRT completed their review of all available clinical safety and PK data for 6 DLT-evaluable subjects in Cohort 1 on 11 May 2017 and determined the dose for the combination therapy cohorts (Cohorts 2 and 4) to be 800 mg andecaliximab Q2W. See Section 1.3 for rationale of dose selection for Cohort 3 (1200 mg andecaliximab Q3W). The internal SRT consisted of Gilead study team members including the Medical Monitor, representatives from Clinical Operations, Drug Safety and Public Health (DSPH), and Biostatistics.

[figure not shown]
Cohorts 2, 3 and 4: Andecaliximab Combination Therapy Cohorts

Japanese subjects with inoperable advanced or recurrent gastric or GEJ tumors will be enrolled in each combination therapy cohort to receive andecaliximab in combination with anti-cancer agents. Dosage and frequency of treatment in these cohorts will be as follows:

- Cohort 2: combination therapy andecaliximab and SP
 - Andecaliximab 800 mg via IV infusion over approximately 30 (\pm 5) minutes Q2W until disease progression. The dose is based on the safety data from Cohort 1. Andecaliximab treatment will be administered in 28-day cycles.

[figure not shown]
- S-1 administered orally twice daily: dosage and regimen will be based on subject condition, investigator discretion, institutional practice and/or the in-country label (see [Figure 3-1](#))
- Cisplatin administered by IV infusion on Day 8 of every 5 weeks: dosage and regimen will be based on subject condition, investigator discretion, institutional practice and/or the in-country label (see [Figure 3-1](#))
- Up to 6 subjects will be enrolled in this cohort

Figure 3-1. Cohort 2 (Combination Therapy Andecaliximab and SP) Proposed Regimen

[figure not shown]
- Cohort 3: combination therapy andecaliximab and SOX
 - Andecaliximab 1200 mg via IV infusion over approximately 30 (\pm 5) minutes Q3W until disease progression. The dose is based on safety data from Cohort 1 and other ongoing Phase 1 studies of andecaliximab. Andecaliximab treatment will be administered in 21-day cycles.
 - S-1 administered orally twice daily at 80 mg/day for body surface area (BSA) $< 1.25\text{m}^2$, 100 mg/day for BSA ≥ 1.25 to $< 1.5\text{m}^2$, and 120 mg/day for BSA $\geq 1.5\text{m}^2$ for the first 14 days of the 21-day cycle (See [Figure 3-2](#))
 - Oxaliplatin administered by IV infusion at 100 mg/m^2 over 2 hours on Day 1 of each 21-day cycle (See [Figure 3-2](#))
 - Up to 10 subjects will be enrolled in this cohort

Figure 3-2. Cohort 3 (Combination Therapy Andecaliximab and SOX) Regimen

- Cohort 4: combination therapy andecaliximab and nivolumab
 - Andecaliximab 800 mg via IV infusion over approximately 30 (\pm 5) minutes Q2W until disease progression. The dose is based on safety data from Cohort 1. Andecaliximab treatment will be administered over in 28-day cycles.
 - Nivolumab 3mg/kg Q2W via IV infusion over 60 (\pm 5) minutes following the completion of andecaliximab administration (See [Figure 3-3](#)). Dose is adjusted if the weight changes more than 10% from the baseline dosing weight.
 - Up to 10 subjects will be enrolled in this cohort

Figure 3-3. Cohort 4 (Combination Therapy Andecaliximab and Nivolumab) Regimen

The cohort dose levels for andecaliximab and associated combination anti-cancer agents are summarized below in [Table 3-1](#):

Table 3-1. Cohort Dose Levels

Cohort	Number of Subjects	Andecaliximab Dose	Andecaliximab Dosing Interval	Combination Anti-Cancer Agent(s)
1	6 to 12	800 mg or 600 mg	Q2W	N/A
2	Up to 6	800 mg	Q2W	SP
3	Up to 10	1200 mg	Q3W	SOX
4	Up to 10	800 mg	Q2W	Nivolumab

Abbreviations: SOX = S-1 and oxaliplatin; SP = S-1 and cisplatin; Q2W = every 2 weeks; Q3W = every 3 weeks

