The dose limiting toxicity (DLT) assessment window is 28 days. The safety and tolerability of the 800 mg dose will be assessed after all 6 subjects have been followed for at least 28 days after the first infusion of andecaliximab. If 2 or more subjects within the cohort of 6 subjects experience DLTs during the first 28 days of andecaliximab dosing, up to 6 additional subjects will be enrolled at a reduced dose of 600 mg Q2W. If a subject is withdrawn from the study for any reason other than a DLT prior to completion of the DLT assessment window, a replacement subject will be enrolled. If 2 additional DLTs occur at 600 mg, andecaliximab will be considered unsafe and will be discontinued.

A DLT is a toxicity defined below, considered possibly related to andecaliximab, occurring during the DLT assessment window (Day 1 through Day 28).

- Grade 4 neutropenia (absolute neutrophil count [ANC] < 500/ μ L) for > 7 days, or febrile neutropenia (per the National Cancer Institute (NCI) Common Terminology Criteria for Adverse Events (CTCAE) Version 4.03 definition) regardless of duration.
- Primary prophylaxis with granulocyte-colony stimulating factor (G-CSF) is not permitted during the first cycle of study treatment. G-CSF may be used at any time at the discretion of the investigator in response to treatment emergent neutropenia. Subjects who develop Grade 4 neutropenia related to andecaliximab will be considered a DLT (subjects may receive G-CSF at the discretion of the investigator in response to treatment emergent neutropenia).
- Grade 4 thrombocytopenia, Grade 3 thrombocytopenia associated with bleeding, or Grade 3 or 4 thrombocytopenia requiring platelet transfusion
- Grade 3 or 4 non-hematologic toxicity (excluding rash, nausea, diarrhea, and vomiting if controlled with standard supportive care)
- Non-hematologic toxicity of \geq Grade 2 (at any time during treatment) that, in the judgment of the investigator and the medical monitor, is dose-limiting
- Treatment delay of > 14 days due to unresolved toxicity

For certain toxicities such as laboratory assessments without a clear clinical correlate, a discussion between the investigator, medical monitor, and the sponsor may take place to determine if this adverse event (AE) should be assessed as a DLT necessitating dose reduction.

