6.3.4. Day 15 of Each 28-Day Cycle

The following will be performed and documented on Day 15 (\pm 1 day):

Pre Dose:

- Modified PE capturing changes from prior examinations and weight
- Vital signs including blood pressure, respiratory rate, pulse, and temperature
- ECOG Performance Status
- Obtain blood and/or urine samples for:
 - Chemistry (See Section 6.12.8)

- Hematology (See Section 6.12.8)
- Coagulation (See Section 6.12.8)
- Andecaliximab concentration (Day 15 of Cycle 1 only) (See Section 6.12.8)
- Blood biomarkers (See Section 3.11)
- Obtain tumor tissue biopsy (Day 15 of Cycle 2 (+5d) only) and perform endoscopic evaluation noting extent and grade of disease and new instances of, or progression of, existing gastritis and dysplasia before biopsies
- Urinalysis (See Section 6.12.8)
- Review of concomitant medication(s)
- Record any SAEs and all AEs related to protocol mandated procedures

Dosing:

- Administer andecaliximab via IV infusion over approximately 30 (\pm 5) minutes

Post Dose: End of Infusion (EOI)

- Obtain blood samples for:
 - Andecaliximab concentration (30 ± 15 minutes, Day 15 of Cycle 1 only) (See Section 6.12.8)
- Record any SAEs and all AEs related to protocol mandated procedures

6.3.5. Cycle 1 Day 29/Cycle 2 Day 1

The Cycle 1 Day 29 visit, which overlaps with the Cycle 2 Day 1 visit, is the end of the DLT assessment window. In order for a subject to be evaluable for the DLT observation, the subject must have received the first dose of andecaliximab, completed all safety procedures through Day 28, or have experienced a DLT prior to Day 28. Assessments should be performed as listed in Section 6.3.1 for Day 1 of each 28-day cycle. Additionally, see Section 6.5 for Continuation of Treatment Assessments.

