6.11. Replacement of Subjects

In Cohort 1 (andecaliximab monotherapy), if a subject is withdrawn from the study for any reason other than a DLT prior to completion of the DLT assessment window, a replacement subject will be enrolled.

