8.3. Data Handling Conventions

By-subject listings will be created for important variables from each eCRF module. Summary tables for continuous variables will contain the following statistics: N (number in population), n (number with data), mean, standard deviation, 90% confidence intervals (CIs) on the mean, median, minimum, and maximum. Summary tables for categorical variables will include: N, n,

percentage, and 90% CIs on the percentage. Unless otherwise indicated, 90% CIs for binary variables will be calculated using the binomial distribution (exact method) and will be 2 sided. Data will be described and summarized by dose level/cohort, analysis set, and time point. As appropriate, changes from baseline to each subsequent time point will be described and summarized. Similarly, as appropriate, the best change from baseline during the study will also be described and summarized. Graphical techniques (eg, waterfall plots, Kaplan-Meier (KM) curves, line plots) may be used when such methods are appropriate and informative.

The baseline value used in each analysis will be the last (most recent) pretreatment value. Data from all sites will be pooled for all analyses. Analyses will be based upon the observed data unless methods for handling missing data are specified. If there is a significant degree of non-normality, analyses may be performed on log-transformed data or nonparametric tests may be applied, as appropriate.

The following censoring conventions will be applied to tumor control endpoints:

- PFS: Data from surviving, non-progressing subjects will be censored at the earliest of the time of initiation of antitumor treatment other than the study treatment or the last time that lack of definitive progression was objectively documented. Data from subjects who have disease progression or die after ≥ 2 consecutive missing tumor assessments will be censored at the last time prior to the missing assessments that lack of definitive disease progression was objectively documented.
- OS: Data from surviving subjects will be censored at the last time that the subject was known to be alive.

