8.6.2. Adverse Events

Clinical and laboratory adverse events will be coded using the Medical Dictionary for Regulatory Activities (MedDRA). System Organ Class (SOC), High-Level Group Term (HLGT), High-Level Term (HLT), Preferred Term, and Lower-Level Term (LLT) will be attached to the clinical database.

Events will be summarized on the basis of the date of onset for the event. A treatment-emergent adverse event will be defined as any adverse event that begins on or after the date of first dose of andecaliximab up to 30 days after the last dose of andecaliximab.

Summaries (number and percentage of subjects) of treatment-emergent adverse events (by SOC, and PT) will be provided by treatment dose level/cohort.

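### SAP 3.1.3 drops from the Cohort 1 DLT set a subject whose Day 15 dose is held for toxicity without a DLT, whom protocol 6.3.5 and the SAP's own appendix count as evaluable

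*Protocol*

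**What the plan says.** **Dosing and window.** Cohort 1 receives andecaliximab on Days 1 and 15 of each 28-day cycle, so the next dose after Day 15 falls on Day 29. The Day 15 visit may move by one day either way (protocol 6.3.4). Protocol 3.2 defines a DLT as a listed toxicity "considered possibly related to andecaliximab occurring during the DLT assessment window (Day 1 through Day 28"). One listed item, also in the synopsis, is "Treatment delay of $>$ 14 days due to unresolved toxicity".

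**Evaluability in the protocol.** Under protocol 6.3.5 an evaluable participant "must have received the first dose of andecaliximab, completed all safety procedures through Day 28, or have experienced a DLT prior to Day 28". Protocol Appendix 2 footnote q and SAP Appendix 1 footnote q say the same. None of the three asks for the Day 15 dose.

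**Evaluability in the SAP.** SAP 3.1.3 offers two routes for Cohort 1 subjects in the Safety Analysis Set. Either all study treatment is completed and safety assessments are available up to and including Day 28, or a DLT occurs strictly before Day 28. SAP 7.1.7.1 uses this set for the Cohort 1 DLT summary.

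**Related rules.** Protocol 5.3.1.1 allows a dose delay for adverse events that are not DLTs, expressly including delays inside the DLT window. Protocol 6.11 provides a replacement only "if a subject is withdrawn from the study for any reason other than a DLT prior to completion of the DLT assessment window". SAP 7.7, on departures from the protocol's safety analyses, mentions only that continuous safety data will not be summarized.

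**The concern.** Requiring completed treatment removes subjects from a toxicity denominator for a reason that can itself be toxicity. A subject held at Day 15 for anemia, uncomplicated Grade 3 neutropenia, or Grade 3 thrombocytopenia without bleeding or transfusion has been observed for the whole window and has shown no DLT. The protocol counts that subject as evaluable. The SAP, read literally, does not.

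The primary objective is safety and tolerability, and the SAP reports that the internal safety review used 6 DLT-evaluable subjects. A final DLT table on fewer than 6 would differ from the basis of that review because of an undeclared definition. The SAP also contradicts its own appendix, so two programmers working from the same SAP could build different sets.

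**Working it through.** **1. The plan's own figure.** Protocol 8.9 and SAP 1.3 state a probability above 65% of seeing 2 or more DLTs in 6 subjects when the true rate exceeds 33.3%. At p = 1/3:

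1 − (2/3)^6 − 6 × (1/3) × (2/3)^5 = 1 − 64/729 − 192/729 = 473/729 = 0.649.

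At p = 0.334 it is 0.650. The figure reproduces and is not in dispute. It assumes a denominator of 6.

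**2. When a held dose becomes a delay DLT.** Days late = day given − day due. The first day more than 14 days late = day due + 15.

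| Dose due | Days late on Day 28 | First day more than 14 late |
|---|---|---|
| Day 14 (early edge of visit window) | 14 | Day 29 |
| Day 15 | 13 | Day 30 |
| Day 16 (late edge) | 12 | Day 31 |
| Day 29 | not yet due | Day 44 |

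A Day 15 dose given on Day 29 is 29 − 15 = 14 days late. That is not more than 14, so it is no delay DLT however the event is dated.

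**3. The two definitions applied.** Each subject below has the first dose and all safety procedures through Day 28.

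| Subject | Protocol 6.3.5 and both footnotes q | SAP 3.1.3 read literally |
|---|---|---|
| Day 15 dose given on time, no DLT | in | in |
| Day 15 dose late but given by Day 28, no DLT | in | in, on the ordinary reading |
| Day 15 dose not given by Day 28, DLT before Day 28 | in | in, by the DLT route |
| Day 15 dose not given by Day 28, no DLT on any criterion | in | **out** |
| Day 15 dose not given by Day 28, first DLT on Day 28 itself | in | **out** |
| Only the Day 29 dose delayed, no DLT | in | in |

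The conflict is confined to the two rows marked out. In the last-day row the event lies inside the protocol 3.2 window but outside the SAP's DLT route. No replacement follows in either row while the subject remains on study.

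**4. Size in an example.** Take six subjects with no DLTs, two of them held at Day 15 and next dosed on Day 29. The protocol gives 0/6. The SAP gives 0/(6 − 2) = 0/4.

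For illustration only, the exact two-sided 90% upper limit for 0/n is 1 − 0.05^(1/n). It is 39.3% for n = 6 and 52.7% for n = 4. Protocol 8.3 sets that interval convention; SAP 7.1.7.1 plans no interval for DLTs.

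**The case against.** Several counter-arguments have force.

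- **The phrase is undefined.** Completing all study treatment could mean not having discontinued, rather than having received every dose. On that reading the conflict disappears. But the SAP does not say so, and its appendix uses different words for the same set.
- **The case is narrow.** Grade 3 or 4 non-hematologic toxicity is generally a DLT, Grade 2 or higher can be judged dose-limiting, and laboratory toxicities can be discussed with the sponsor. Any of these before Day 28 brings the subject in by the DLT route. What remains is mainly the hematologic events named above.
- **The exclusion would not be hidden.** SAP 3.1 plans the number and percentage of subjects in each analysis set by cohort, and a listing of exclusion reasons. The dosing listing and the adverse event interruption outputs would also show the hold.

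A reader might infer something stronger from the arithmetic in step 2: that the delay criterion can never be met inside the window, so a subject held more than 14 days could be reported as 1/6, 0/6 or 0/5. The documents do not support that. Protocol 3.2 places the toxicity, not the confirmation of its consequence, in the window. The Grade 4 neutropenia criterion lasting more than 7 days works the same way, since an episode starting late in the window is also confirmed after it. Protocol 8.6.2 adds: "Events will be summarized on the basis of the date of onset for the event". On this natural reading, a toxicity starting before Day 28 that delays the dose by more than 14 days is a DLT, enters by the SAP's DLT route, and counts as 1/6 under both documents. An explicit sentence for the delay item is missing, but only as a detail.

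**Conclusion.** The inconsistency is real and minor. SAP 3.1.3 imposes a treatment-completion condition that protocol 6.3.5, protocol Appendix 2 footnote q and SAP Appendix 1 footnote q do not, and SAP 7.7 does not declare it.

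Each affected subject lowers the reported DLT denominator by one. This rests on a literal reading of SAP 3.1.3, a Day 15 dose still not given by Day 28, and no DLT before Day 28. The documents do not say how many Day 15 doses were held. If none was held through Day 28, no reported number changes.

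It would also be wrong to infer that the dose choice is in doubt. The review of 6 DLT-evaluable subjects was completed on 11 May 2017 and selected 800 mg every 2 weeks for Cohorts 2 and 4. The SAP definition bears only on the final tables.

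**What to change.** 1. **Amend SAP 3.1.3** so that Cohort 1 subjects with the first dose and the required safety assessments through Day 28 stay in the DLT Analysis Set, whether or not the Day 15 dose was held. This matches protocol 6.3.5 and SAP Appendix 1 footnote q.
2. **Let a DLT on Day 28 qualify**, citing the window in protocol 3.2. This clause rests on that window alone, because protocol 6.3.5 and the footnotes also refer to a DLT before Day 28.
3. **Add one line to SAP 7.1.7.1**: a delay DLT is attributed to the window by the onset of the toxicity that caused it, even if the delay passes 14 days later.

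The cost is a few words. If the SAP is already final, its Section 1 provides for documenting the change in the clinical study report. No protocol amendment, new data or supplementary DLT count is needed.
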